## PROJECT TITLE:

Effectiveness of Electrical Neurostimulation as an Opioid-Sparing Alternative in the Treatment of Cyclic Vomiting Syndrome.

PI NAME	[name]	
CO-PI NAME(s)	[name]	
Co-Investigators	[name] [name]	

NCT#: NCT04721171

Document Date: 02/18/2019

Cyclic vomiting syndrome (CVS) is a chronic functional gastrointestinal disorder (FGID) characterized by episodic nausea, vomiting and severe abdominal pain in majority (80%) of patients. Most patients also have a migraine headache, photophobia, phonophobia and lethargy during an episode. The pathophysiology of CVS is not known but is thought to be a migraine diathesis given the overlap between the two syndromes. Various factors such as mitochondrial DNA polymorphisms, genetic variants in the cannabinoid receptor genes and and calcitonin gene-related peptide (CGRP) are thought to play key roles.

CVS is common and affects 2% of the population in the US. The disorder is disabling, and healthcare costs associated with CVS hospitalizations in adults are staggering, amounting to \$200 million dollars bi-annually. Due to sub-optimal therapies, hospitalized patients are usually treated empirically with IV fluids, anti-emetics, benzodiazepines and opioids for the intense abdominal pain. Unfortunately, opiate therapy in CVS is fraught with problems and is a risk factor for recurrent hospitalizations (preliminary data) as well as non-response to prophylactic therapy. Additionally, use of opioids is associated with dependence, withdrawal, addiction, overdose and even death. Hence, there is a critical need for safe, opiate-sparing strategies to treat pain associated with CVS episodes. Neurostimulation via a novel auricular percutaneous electrical nerve field stimulation (PENFS) device has recently emerged as a safe and non-invasive therapy for the treatment of pain, nausea and vomiting disorders. This therapy was recently FDA-approved for the symptoms of opioid withdrawal. Preliminary data indicates that PENFS modulates peripheral vagal nerve signaling, likely also modulating the trigeminal pathway from the external ear to the brainstem.

We hypothesize that 1) **PENFS** is a safe, non-invasive opioid-sparing alternative therapy for the severe abdominal pain, nausea and vomiting associated with CVS. We also hypothesize that 2) PENFS reduces length of stay (LOS), and improves patient satisfaction. We propose the following specific aim:

# Aim 1. Investigate the efficacy of PENFS compared to a sham in hospitalized patients with CVS

## **Objective 1:**

- a. Demonstrate reduction in abdominal pain, nausea and vomiting using validated tools.
- b. Obviate or reduce the need for opioids.
- c. Reduce length of hospital stay and improve patient satisfaction.

This approach will specifically address the current opioid problem using a novel, non-invasive neurostimulation therapy with proven efficacy for opioid withdrawal. Long-term, it may improve health care outcomes and significantly reduce overall health care costs.

#### (A) Significance

Cyclic vomiting syndrome (CVS) is a chronic functional gastrointestinal disorder (FGID) that is characterized by episodic nausea, vomiting and abdominal pain and is a significant health care problem. It affects 2% of the U.S. population and imposes an enormous burden on patients and the health care system. Due to the recalcitrant nature of the disease, patients have high rates of health care utilization with multiple emergency department visits and hospitalizations. These in turn lead to school and work absenteeism, job loss, divorce, and disability. The economic impact of CVS is staggering amounting to > \$200 million over 2 years, based on a nationwide study.

CVS is associated with multiple comorbid conditions such as migraine headaches, autonomic dysfunction, anxiety and depression, which further contribute to disease severity. A personal and family history of migraine is present in 87% of patients. CVS is considered a migraine equivalent given the striking similarities between the two disorders such as periodicity, response to medications like amitriptyline and triptans and common symptoms such as nausea, vomiting, photo- and phono-sensivtivity. Both migraine and CVS are also triggered by sleep deprivation and stress. A recent brain imaging study demonstrates similarities in functional connectivity of the insular region in CVS and migraine, further solidifying the link between these disorders. These data suggest that *CVS and migraine share similar pathophysiology* and potential for a common therapeutic avenue.

## Opioid use in CVS and the critical need for opioid sparing therapy

Given the lack of knowledge about pathophysiology and evidence-based therapies, patients are often hospitalized to treat symptoms of CVS. During an episode, patients present with severe vomiting and abdominal pain and are treated empirically with IV fluids, antiemetics, benzodiazepines, and opioids. Estimates of opioid use range from 23%-27% in adults with CVS. Patients are often dissatisfied with the level of analgesia as recurrent opioid use results in tolerance and dependence. This often undermines the physician-patient relationship and patients even leave against medical advice out of frustration with what they perceive as ineffective care. This can lead to worse outcomes including recurrent hospitalizations, morbidity and increased health care costs.

Preliminary data from a study by our group reveals that of 101 patients hospitalized with CVS at Froedtert Hospital, chronic opioid therapy is associated with a two-fold increased risk of hospitalization (RR 2.22, CI 1.1-4.4, P=0.02) and three-fold increase in hospital length of stay (LOS) (RR 3.43, CI 1.26-9.34, P=0.01). In a study of 132 CVS patients, opioid use was associated with non-response to amitriptyline (53% vs 15%, p<0.05), a prophylactic therapy used in CVS. In turn was associated with increased frequency and duration of CVS episodes per year and increased number of hospitalizations/emergency

department (ED) visits at baseline (18% vs 15.2%, p<0.05). Hence there is an urgent need for an opioid-sparing, non-invasive strategy to treat CVS symptoms.

In summary, CVS is common and disabling and is associated with significant health care costs. Much of this burden can be tied to iatrogenic opioid overuse, resulting in chronic opioid use and high risk of addiction and health care utilization. Understanding the pathophysiology of CVS and development of novel therapies are urgently needed. Further, similar to other disorders with rampant opioid use, **there is a critical need for opioid-sparing therapy in CVS to negate the devastating short and long-term effects of opioid use**. Our proposed project using a novel, non-invasive device to treat CVS will also address the current opioid crisis.

#### Auricular neurostimulation: a novel treatment modality in CVS

The major role of the arousal neurocircuitry in nausea and vomiting is well established. Similar to migraines, stress and neuronal excitability may trigger CVS episodes. Various neurostimulation modalities have emerged as therapy for gastrointestinal disorders and migraines but most options are invasive. The effects are believed to be mediated via increased vagal afference to the brainstem nucleus tractus solitarius (NTS) and modulation of the trigemino-autonomic reflex, influencing higher cortex. Pacing studies confirm that the ear contains branches of four cranial nerves (CN V, VII, IX, X) that project to the NTS, providing a conduit for stimulation of NTS. Animal and human data show that transcutaneous stimulation of the vagus nerve (CN X) in the ear transmits signals to the NTS and improves migraine, presumably via modulation of trigemino-cervical complex (TCC). Neuroimaging studies show that this therapy modulates brainstem and limbic brain regions such as the amygdala, a region involved in stress and fear signaling. NTS activation, modulating the TCC and limbic regions.

[figure not shown]

Fig 1: Bridge device

More recently, the Bridge device, a non-invasive percutaneous electrical nerve field stimulation (PENFS) applied to the external ear, has demonstrated efficacy in treating pain, nausea and vomiting in opioid addiction (Fig. 1). A large, randomized sham-controlled trial also demonstrated significant improvement in abdominal pain, well-being and disability in adolescent FGIDs. Based on neuronal tracing studies, PENFS likely modulates the vagus and the trigeminal nerves which project to the external ear. Branches of these nerves converge in the brainstem NTS and signal to higher brain regions (amygdala, hypothalamus). Recent data has also shown that PENFS modulates

neurons of the central amygdala and improves visceral sensitivity in an animal model. We propose that the neurostimulation of cranial nerves through the PENFS device will alleviate

CVS symptoms by modulating the neurocircuitry pathway involved in the pathogenesis of the disease.

#### B) Innovation, Novel Technology and/or Novel Approach

#### **PENFS: a novel technology for the treatment of CVS**

The Bridge device (PENFS) is a novel technology that is designed to treat pain and also improves other symptoms such as nausea and vomiting. The Bridge device has recently been approved by the FDA for treating opioid withdrawal symptoms including pain, nausea, vomiting, insomnia and agitation. Most recently, it has also been shown to be a safe and effective therapeutic option for adolescents with abdominal pain-related functional gastrointestinal disorders, resulting in reduction in abdominal pain and global symptom imrovement. *If our study shows the efficacy of the Bridge device compared to sham in mitigating pain, nausea and vomiting, it will have the potential to transform the clinical care of CVS patients with the advent of an innovative, opiate sparing, non-invasive technology.* Further, our purposed device through its effectiveness in resolution of symptoms will improve *patient satisfaction*, reduce hospital LOS and overall health care costs. *More importantly, it will address the current opioid crisis that affects patients with CVS and potentially can be applied to other chronic disorders associated with pain.* 

In summary, our study attempts to **shift the current clinical practice paradigm** in CVS and enhance our understanding of the pathophysiology through the use of PENFS device as a novel, non-invasive **approach in mitigating the detrimental effects from opioids** in CVS. Additionally, this device can also be used in the treatment of other chronic pain disorders.

## (C) Approach, Feasibility, and Environment

## Aim 1: Investigate the efficacy of PENFS in adults admitted with cyclic vomiting syndrome

## Methods

**Inclusion/Exclusion Criteria.** We will enroll 80 adults between the ages of 18-65 years with a diagnosis of CVS (based on Rome IV diagnostic criteria). This study will only include patients who are admitted to Froedtert Hospital with an episode of CVS. Exclusion

criteria includes developmental delays, non-English speaking patients, pregnancy, any implanted electrical device or any significant dermatological/infectious condition of the ear.

Randomization. Subjects will be randomized to the intervention group (receiving the Bridge device) or control group (receiving an identical sham device lacking electrical charge) in 1:1 ratio. The auricular neurostimulator device will be placed on the subject's ear upon presentation to the hospital. The device delivers low voltage (3.2), continuous stimulation for 5 days (around the clock) in alternating frequencies (1-10Hz) with an impulse interval of 100ms/2 sec. The neurostimulators (for both treatment arms) will be placed by a certified MD/APP/RN inside the patient's room. All patients will be allowed to receive rescue medications after implantation of the device if the symptoms do not improve with the device or at patient's request.

We have performed a sample size calculation based on prior data. At a significance level of 0.05 and 80% power, we estimate a sample size of 40 participants per group to detect the minimum standardized effect size of 0.64 using two-sided tests, using prior data. We will compare the different variables (average daily reduction in abdominal pain, nausea/vomiting scores, average daily use/frequency/dosage of rescue medications (opiates, antiemetics and sedatives between PENFS vs sham device.

Outcomes. Primary outcome will include the change in abdominal pain and concurrent opioid use. Abdominal pain will be assessed daily through Visual Analog Scale with the score ranging from 0 to 10, with 0 being the least and 10 being the worst pain. The need for opiates will be assessed through- (a) the time taken by the subject from the time of admission to the first felt need accompanied by the actual administration of opiates (IV hydromorphone or morphine), (b) daily frequency and total dosage of opiates received. Secondary outcomes will include- (a) severity of daily nausea and vomiting assessed through the Index for Nausea, Vomiting and Retching (INVR); (b) the need for other rescue medications (which include antiemetics like ondansetron, promethazine & metoclopramide; benzodiazepines like lorazepam; antihistaminics like diphenhydramine, etc.), (c) hospital LOS and (d) survey on patient satisfaction. While all other outcomes will be assessed daily, LOS and patient satisfaction will be assessed at the time of discharge (Table 1). All variables will be compared between the subjects in intervention arm versus control arm.

We hypothesize that PENFS will effectively mitigate the abdominal pain, nausea and vomiting associated with CVS episodes, obviate or reduce the need for opiates and simultaneously improve healthcare outcomes including LOS and patient satisfaction.

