**Table 1. Study Protocol** 

Tubic 1. Study	1100001					
	Admission (0 hours)	2 hours post - placement	24 hrs.	Daily	5 days*	Discharge
Screening & Consent	X					

Demographics	X					
Neurostimulator (PENFS) vs sham	X	X	X	X	X	
Rome IV questionnaire 	X					
INVR (vomiting scale; daily during therapy) 	X	X	X	X	X	X
Abdominal pain (Visual Analogue Scale)	X	X	X	X	X	X
Need for opiates and other rescue medications	X	X	X	X	X	X
Length of stay						X
Patient Satisfaction Survey						X

INVR=Rhodes Index of Nausea, Vomiting & Retching; CGRP= Calcitonin Gene-Related Peptide

**Statistical Analysis:** Summary statistics, such as mean, median, standard deviation and range will be used as a first step to examine data. To satisfy parametric assumptions, we may perform transformations with justifications if possible and otherwise use non-parametric tests. For any binary outcomes, we will use Chi-square or Fisher's exact tests to compare the proportions between the two groups. We will compare the different variables (average daily reduction in abdominal pain, nausea/vomiting scores, average daily use/frequency/dosage of rescue medications (opiates, antiemetics and sedatives) between PENFS vs sham device. Data analyses will be performed using SAS version 9.4 (SAS institute, Cary, NC).

**Potential Pitfalls:** This pilot data is both safe and non-invasive and will help us better understand the pathophysiology underlying CVS symptoms. The proposed device is non-invasive and currently utilized at our institution. The PI is certified in the PENFS placement and has already used it in some of her patients with success. We thus expect no feasibility or safety issues. Potential risks generally would include bleeding or infection at the puncture site, pain at the application site, or skin irritation at the site of application.

**Feasibility**: Recruitment should not pose a problem as the PI ([name]) has the largest cohort of patients with CVS in the nation. Further in our experience, CVS sufferers are also highly motivated to enroll in studies and trial new therapies The PI also works closely with the Cyclic Vomiting Syndrome Association, who will advertise the study on their website and

\* questionnaires will be completed as an outpatient if patient is already discharged

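### Previous use of the Bridge/PENFS device is neither an exclusion nor recorded, although the device is already in use at the institution; any prior users who enrol could weaken patient masking

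*Combined protocol and SAP*

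**What the plan says.** All references are to the combined protocol and SAP.

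- **Eligibility (Methods, Inclusion/Exclusion Criteria).** Adults aged 18 to 65 with Rome IV CVS qualify, and "This study will only include patients who are admitted to Froedtert Hospital with an episode of CVS". The exclusion text reads "criteria includes developmental delays, non-English speaking patients, pregnancy, any implanted electrical device or any significant dermatological/infectious condition of the ear". Neither part asks that a patient be new to the device.
- **Control (Methods, Randomization).** Patients go to the Bridge device or to a "control group (receiving an identical sham device lacking electrical charge) in 1:1 ratio". Rescue medication is allowed if symptoms do not improve or when the patient asks for it.
- **Existing use (Potential Pitfalls).** "The proposed device is non-invasive and currently utilized at our institution". The next sentence adds: "The PI is certified in the PENFS placement and has already used it in some of her patients with success".
- **Recruitment (Feasibility).** Recruitment is expected to be easy because the principal investigator "has the largest cohort of patients with CVS in the nation".
- **Outcomes.** The primary outcome is change in abdominal pain on a 0 to 10 visual analogue scale, together with opioid use (time to first opioid, daily frequency and total dosage).
- **Data collection and analysis.** Table 1 lists consent, demographics, the Rome IV questionnaire, symptom scores, rescue medication, length of stay and satisfaction. It has no item for device history. The Statistical Analysis text compares the two groups without mentioning previous use.

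**The concern.** A sham identical to the active device except for the missing charge masks patients only if they cannot tell stimulation from its absence. Someone who has worn the active device has a memory to compare against, and is the patient most likely to guess correctly. The eligibility rule lets such patients in. The plan's own text shows that some people have worn the device, and that their treating physician's cohort feeds the trial.

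The outcomes at stake are the primary ones. Pain is self-rated, and opioids can be given on request. A patient who recognises the sham will tend to rate pain worse or ask for opioids sooner; one who recognises active stimulation will tend to do the opposite. Both favour the device. Randomization balances the number of prior users between arms but does not remove this bias, because the reaction differs by arm. Earlier opioids could also lower pain scores in sham patients, so the effect may appear partly in pain and partly in opioid use.

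Because previous use is never recorded, the finished trial could not show whether the problem was trivial.

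**Working it through.** **1. The plan's own figure.** Inputs from Methods: two-sided alpha 0.05, power 80%, standardized effect 0.64, allocation 1:1. The normal approximation gives n = 2 × (1.960 + 0.842)² / 0.64² = 2 × 7.85 / 0.4096 = 38.3, so 39 per group. The two-sample t-test gives 39.3, so 40 per group, with 80.7% power at 40. The stated 40 per group is reproduced, and this point does not dispute it.

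**2. Bias model.** Let f be the share of each arm that has worn the active device. Let b be the extra difference between arms, in SD, among those patients because they know or suspect their allocation. With no true effect, the false difference is d = f × b. With 40 per arm the test statistic is shifted by d × √(40/2) = d × √20 = 4.472d. The two-sided rejection probability is Φ(−1.96 + 4.472d) + Φ(−1.96 − 4.472d).

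**3. Inputs.** The documents give neither f nor b. Both are assumed: f = 5% to 25% (4 to 20 of the 80 patients) and b = 0.5 to 0.8 SD.

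| f | b (SD) | d = f × b (SD) | shift 4.472d | two-sided type I error | d / 0.64 |
|---|---|---|---|---|---|
| 5% | 0.5 | 0.025 | 0.112 | 5.1% | 4% |
| 5% | 0.8 | 0.040 | 0.179 | 5.4% | 6% |
| 10% | 0.5 | 0.050 | 0.224 | 5.6% | 8% |
| 10% | 0.8 | 0.080 | 0.358 | 6.5% | 13% |
| 25% | 0.5 | 0.125 | 0.559 | 8.6% | 20% |
| 25% | 0.8 | 0.200 | 0.894 | 14.5% | 31% |

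The exact noncentral t with 78 degrees of freedom gives 5.1% in the first row and 14.3% in the last, so the approximation is adequate.

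**4. Recruitment cost of an exclusion.** The timeline gives about 180 CVS admissions a year, or 180/12 = 15 a month, against a target of 12 a month (12/15 = 80%). Treat these as distinct, otherwise eligible patients who all consent, which is generous. Then:

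- Without the exclusion, 80 patients take 80/15 = 5.3 months.
- Excluding 5% leaves 14.25 a month, so 80/14.25 = 5.6 months.
- Excluding 25% leaves 11.25 a month, so 80/11.25 = 7.1 months.
- The target of 12 a month becomes unreachable once the excluded share passes 1 − 12/15 = 20%.

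So the share of prior users drives both the bias and the cost of removing it. If they are few, the bias is small and exclusion costs almost nothing. If they are many, the bias matters and exclusion slows enrolment.

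**The case against.** The strongest reply is that the chain from eligibility rule to biased result has several links the documents do not supply.

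- **Who was treated.** The text speaks of some of the principal investigator's patients. It gives no number and no diagnosis, and the FDA approval it cites is for opioid withdrawal. A reader might infer that these were CVS patients. That is reasonable given the investigator's cohort, but it is not stated. The text also says use at the institution, not specifically at Froedtert Hospital.
- **Whether all responded.** A reader might infer that the trial would be enriched with known responders. Use with success in some patients does not say that each one responded, so this reading is not supported.
- **Whether stimulation can be felt.** The plan describes low-voltage stimulation and never says whether it is perceptible. An identical percutaneous sham may cause local sensation of its own. If stimulation is obvious, naive patients may notice it too, and excluding prior users would not cure that.
- **Whether the blind fails.** A reader might go further and conclude that it does. The documents support only a risk of partial unmasking in a subgroup of unknown size. They never formally say that this trial is blinded, or who would be; the identical sham implies patient masking and no more.
- **Re-enrolment.** A returning patient could in principle be randomized twice, but 80 adults and 40 participants per group most naturally mean distinct people. This is a minor clarification.

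These replies limit the strength of the point and leave the size open. They do not remove the omission, which is visible in the eligibility text, Table 1 and the analysis text and is not a product of redaction.

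**Conclusion.** The point holds in a limited form. Prior users of the device can be enrolled, and nothing records that they were, at an institution where the device is in use and with recruitment drawn from the cohort of a physician who has used it. Any who enrol may guess their allocation better than others, which threatens patient masking of self-rated pain and on-request opioid use and would tend to favour the device.

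The consequence runs from negligible (0.025 SD, type I error 5.1%) to material (0.20 SD, type I error about 14.5%). That range rests wholly on the assumed shares and shifts, on stimulation being perceptible, and on patients reacting in the expected direction. The low end is at least as credible as the high end, since the text speaks only of some patients. Confidence is high that the omission exists and moderate that it matters. It is a cheap improvement and does not invalidate the design.

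**What to change.** 1. Add to the exclusions in Methods: previous use of the Bridge/PENFS device or another auricular stimulator.
2. Add a question on previous use to the screening row of Table 1.
3. State that each patient is randomized once.

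If screening shows that exclusion would cost too many patients, record previous use instead, stratify the randomization on it, and report a sensitivity analysis restricted to device-naive patients.

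The cost is one line of eligibility text, one screening question and the loss of an unknown, probably small, number of admissions. The sample size of 40 per group does not change.

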through email and supports this project. Co-PI ([name]) and [name] have worked extensively with the PI and published collaboratively in the field. [name], the Section Chief, along with [name], both hospitalists, are aware and will oversee all the logistics regarding the admissions and the study, as CVS patients are typically admitted under Hospitalist service. In a recent neurostimulation trial conducted by [name], a high degree of compliance and a low dropout rate (12%) was observed despite a sham-controlled study design. Patient satisfaction with this non-pharmacological therapy was extremely high.

In summary, this proposal will evaluate a novel, safe and non-invasive therapy for a debilitating and prevalent disorder with few established treatment options. Demonstrating that this therapy is effective in treating and preventing CVS via neuromodulation will allow us to apply for extramural funding and expand our studies to a larger number of CVS patients and possibly other conditions.

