## (D) Special Emphasis

Patients who are admitted to the hospital with a CVS episode typically suffer from intense abdominal pain. Opiates with anxiolytic properties are therefore particularly effective in controlling symptoms in patients with CVS. Consequently, patients admitted with a CVS episode frequently require treatment with intravenous opioids. The addictive potential of narcotic pain medications is well known. As with other acute painful conditions, the use of opioids during a CVS episode may be followed by ongoing use of opioids. Also, withdrawal from opiates may be equivalent to a panic trigger for another exacerbation for a CVS episode. Therefore, patients are often reluctant to give up using opiates on an ongoing basis. Ongoing use of opioids in turn leads to disease coalescence with opioid dependence and withdrawal leading to recurrent episodes of CVS exacerbation. Escalating use of opiates can also lead to narcotic bowel syndrome which is characterized by worsening bouts of abdominal pain induced by opioid-induced bowel dysfunction.

The main focus of our study is to replace the need for intravenous opiates during a CVS episode with a non-invasive and safe device that can be placed with ease and does not require specific expertise.

- 7. Sunku B, Li BUK . Cyclic vomiting syndrome. In: Guandalini S, editor. Textbook of Pediatric Gastroenterology and Nutrition. London, United Kingdom: Taylor and Francis Group; 2004. pp. 289–302.

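### Bleeding at the puncture site is a declared device risk, but no exclusion or screening item asks about a bleeding disorder

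*Combined protocol and SAP*

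**What the plan says.** Inclusion is limited to adults aged 18 to 65 who meet Rome IV criteria for CVS and are admitted with an episode (section (C), Inclusion/Exclusion Criteria). The exclusion "criteria includes developmental delays, non-English speaking patients, pregnancy, any implanted electrical device or any significant dermatological/infectious condition of the ear".

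The Potential Pitfalls paragraph after Table 1 states: "We thus expect no feasibility or safety issues. Potential risks generally would include bleeding or infection at the puncture site". It goes on to list pain and skin irritation where the device is applied.

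Under Randomization, the device goes on the ear when the patient presents to hospital, and "The neurostimulators (for both treatment arms) will be placed by a certified MD/APP/RN". The device is meant to run day and night for five days. Controls are described as "receiving an identical sham device lacking electrical charge".

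Table 1 has a single combined row for screening and consent, at hour 0, with no detail of what screening covers.

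**The concern.** The plan declares a hazard and then gives no written means of keeping out the patients most exposed to it. Its other patient-dependent device hazards do have a matching exclusion: ear infection, ear skin disease and implanted electronics are all listed. Bleeding is not.

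What is at stake is patient safety on a small scale: avoidable bleeding at the ear in someone whose tendency to bleed was already known. Nothing downstream would make up for a missed screen. The Outcomes paragraph lists no safety outcome and Table 1 has no adverse-event row, so the check before placement is the natural place to deal with this.

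**Working it through.** The point concerns eligibility text, so the main check is to set each declared hazard beside the criteria.

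| Hazard | Where it arises | Matching exclusion |
|---|---|---|
| Infection at the puncture | Potential Pitfalls | Infectious ear condition |
| Skin irritation | Potential Pitfalls | Dermatological ear condition |
| Electrical stimulation | Nature of the device | Implanted electrical device |
| Pain where applied | Potential Pitfalls | None |
| Bleeding at the puncture | Potential Pitfalls | None |

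Pain has no matching exclusion either, but the plan points to no prior trait that would predict it. Bleeding does have one, and a history question finds it.

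**Where a screen could sit.**
- Exclusions: developmental delay, language, pregnancy, implanted device, ear condition. That is 5, of which 0 concern bleeding.
- Table 1 rows: screening and consent, demographics, device or sham, Rome IV, INVR, pain, opiates and rescue drugs, length of stay, satisfaction. That is 9, of which 0 name a bleeding history.
- The inclusion criteria do not touch bleeding, and no other section states a screen or an investigator-discretion clause.

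**Exposure.** The criteria govern 80 patients. At 1:1, 80 / 2 = 40 receive the active device, each for up to 5 × 24 = 120 hours. Two further points are inferences. The sham is called identical, so it may puncture the skin too. The Table 1 footnote says "questionnaires will be completed as an outpatient if patient is already discharged", so part of the wear time may fall after discharge.

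**Effect on the sample size.** The stated 40 per group reproduces. With a standardized effect of 0.64, two-sided alpha 0.05 and 80% power, n = 2 × (1.960 + 0.842)² / 0.64² = 38.3, so 39 per group by the normal approximation. The t-test version gives 39.3, so 40. A new exclusion enters none of these inputs.

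**Size of the risk.** The documents give no prevalence of bleeding disorders or anticoagulant use among CVS admissions, and no bleeding rate or grade. Purely as an assumption, let the prevalence of a known bleeding disorder be p. The chance of at least one such patient among 80 is 1 − (1 − p)^80:

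| Assumed p | Expected patients (80p) | Chance of at least one |
|---|---|---|
| 0.1% | 0.08 | 8% |
| 0.5% | 0.4 | 33% |
| 1% | 0.8 | 55% |
| 2% | 1.6 | 80% |

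This shows how often the question might matter at enrolment. It does not measure harm.

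**The case against.** Five objections deserve an answer.

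1. **The list may not be exhaustive.** It is introduced with a word that can mean a partial list, and the document reads as a pilot-funding application with the IRB submission still in progress. That is a fair caution. But no fuller list is shown, and an unwritten criterion cannot be applied uniformly. Consent pages are absent from the public copy, so a warning there cannot be ruled out; a warning would still not be an eligibility rule.
2. **Table 1 does not itemise screening.** This is correct. None of the five listed exclusions has its own row, so the table's silence proves little. The weight rests on the exclusion list.
3. **Trained clinicians place the device.** Placement is by certified staff, training is planned in the Project Timeline, the device is already in use at the institution, and "CVS patients are typically admitted under Hospitalist service". Some clinical judgement before placement is plausible. It remains a partial safeguard, because no text assigns a bleeding check. Special Emphasis calls this "a non-invasive and safe device that can be placed with ease and does not require specific expertise", but that is promotional wording and should not be used to discount the certified-placer rule.
4. **A listed risk need not have an exclusion, and this one is small.** The smallness stands. The project summary says these inpatients usually receive IV fluids, so they have other skin punctures anyway. That supports a minor rating but does not supply the missing check.
5. **Excluding bleeding disorders while only reviewing anticoagulated patients is uneven.** This has force. The documents give no basis for the distinction, and clinician review for both would also close the gap.

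**Conclusion.** The concern holds as a minor patient-safety point. The eligibility rules as written admit a patient with a known bleeding disorder to a trial of a skin-puncturing device for which the plan itself lists bleeding as a risk. The size of that risk cannot be calculated from the documents; the added hazard over ordinary inpatient care may well be small. Power, alpha and the efficacy analysis are unaffected.

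The conclusion assumes that the printed exclusion list is the one staff will apply, and that no unseen training material or device labelling already requires a bleeding check. If either assumption is wrong, the gap is one of documentation only.

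**What to change.** Add known bleeding disorder to the exclusions, next to the ear-condition entry. Within the existing screening and consent step, before the active or sham device is placed, ask about a known bleeding disorder and about therapeutic anticoagulation. A yes on anticoagulation goes to clinician review, not automatic exclusion, to limit the loss of patients. If the sponsor would rather not exclude mild disorders outright, written clinician review for both conditions would be an acceptable alternative.

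The cost is one phrase, one history question and one review step, with no new visit or laboratory test. Results would not extend to patients with a bleeding disorder.

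Recruitment room is limited. The Project Timeline gives about 180 patients admitted a year, or 180 / 12 = 15 a month, before other exclusions and refusals. The target of 12 a month is 12 / 15 = 80% of that, leaving 15 − 12 = 3 a month for all losses together. That target is listed only for March and April 2019, so the monthly margin should not be read as an annual one. If 12 a month is achieved, each replaced patient adds about 30.4 / 12 = 2.5 days.
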